HCC	Hepatocellular carcinoma
HCV	Hepatitis C virus
HDPE	High-Density Polyethylene
HRPP	Human Research Protections Program
HR	Hazard Ratio
ICIs	Immune Checkpoint Inhibitors
IHC	Immunohistochemistry
IL-2	Interleukin-2
IND	Investigational New Drug
INR	International normalized ratio
irAEs	Immune-Related Adverse Events
iRECIST	Immune Response Evaluation Criteria in Solid Tumors
IV (or iv)	Intravenously

LD	Longest Diameter
LOAEL	Lowest-observed-adverse-effect level
MI	Molecular Intelligence
mRECIST	Modified Response Evaluation Criteria in Solid Tumors
MRI	Magnetic Resonance Imaging
MTD	Maximum Tolerated Dose
NCI	National Cancer Institute
NE	Not Evaluable
NOAEL	No-observed-adverse-effect level
ORR	Objective Response Rate
OS	Overall Survival
PBMCs	Peripheral Blood Mononuclear Cells
pCR	Pathologic Complete Response
PD	Progressive Disease
PD-1	Programmed cell Death protein 1
PD-L1	Programmed Death-Ligand 1
PET	Positron Emission Tomography
PFS	Progression Free Survival
PK	Pharmacokinetic
PO	peros/by mouth/orally
PR	Partial Response
PS	Phosphatidylserine
PT	Prothrombin time
RCC	Renal Cell Carcinoma
RECIST	Response Evaluation Criteria in Solid Tumors
SAE	Serious Adverse Event
SCCC	Simmons Comprehensive Cancer Center
SD	Stable Disease
SGOT	Serum Glutamic Oxaloacetic Transaminase
SLD	Sum of the Longest Diameter
SPGT	Serum Glutamic Pyruvic Transaminase
SVR12	Sustained Virologic Response after 12 weeks post-treatment
TK	Toxicokinetic
USP	United States Pharmacopeia
VEGF	Vascular Endothelial Growth Factor
VEGFR	Vascular Endothelial Growth Factor Receptors
WBC	White Blood Cells

STUDY SCHEMA

*The first 6 patients enrolled who have received at least 1 cycle of treatment will be considered a safety lead-in.

STUDY SUMMARY

Title	Multi-center phase II open-label study of baviximab, axitinib, and avelumab in advanced hepatocellular carcinoma
Short Title	Phase II study of baviximab, axitinib, and avelumab in advanced hepatocellular carcinoma
Protocol Number	TBD
Phase	Phase 2 with safety lead-in
Methodology	Open-label
Study Duration	24 months accrual/24 months follow-up
Study Center(s)	UT Southwestern Medical Center and Parkland Health and Hospital System
Objectives	To determine the objective response rate of combination axitinib, avelumab, and baviximab in advanced HCC not previously treated with systemic therapy.
Number of Subjects	14-29 evaluable patients

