4.2.1 Safety Lead-in and Dose-limiting Toxicities

A safety and tolerability assessment will be performed for patients treated with axitinib, bavituximab, and avelumab after the first 6 patients evaluable for dose-limiting toxicities have completed 1 cycle (ie, Cycle 1 Day 28). Patients will be considered evaluable for dose-limiting toxicities assessment if they have completed all scheduled study visits during the first cycle and have received 2 (100%) of the 2 planned doses of avelumab and at least 3 (75%) of the 4 planned doses of bavituximab in Cycle 1.

Dose-limiting toxicities are defined as any Grade 3 or greater AE that occurs during the first cycle (28 days) and are considered to be related (possible, probable, or definite) to study drug, specifying attribution to axitinib, avelumab, bavituximab, or all drugs. Intolerable Grade 2 gastrointestinal toxicities (such as persistent nausea/vomiting or diarrhea) will also be considered dose-limiting toxicities if they are considered to be related to any study drug. See Tables 2 and 3 below and Section 7.0 for AEs associated with axitinib, avelumab, or bavituximab.

Enrollment of additional patients after the first 6 potentially evaluable patients for dose limiting toxicities will be suspended until after assessment of the safety lead-in phase by the UTSW Simmons Cancer Center Gastrointestinal Disease-Oriented Teams (GI DOT) is complete.

- If ≤ 1 dose-limiting toxicity occurs, trial enrollment will proceed without any modifications.
- If ≥ 2 dose-limiting toxicities occurs, all treatment-related AEs will be reviewed by the GI DOT for consideration of modification or termination of the study. Modifications may include reducing the starting dose of axitinib by one dose level to 3 mg BID for all subsequent patients enrolled and not permitting dose re-escalation above dose level 0.

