	3	For first and subsequent occurrence, withhold until BP is less than 150/100 mm Hg and adjust antihypertensive medication. Then, reduce by 1 dose level and resume treatment.	Continue as per schedule.	Continue as per schedule.

		
If on maximal anti-hypertensive treatment, reduce by 1 dose level.
 
If axitinib dosing is interrupted, patients receiving antihypertensive medications should be monitored closely for hypotension as BP usually decreases within 1-2 days after the last dose.
		
	4	
Repeat dose reduction by one lower dose level.
 
Permanent discontinuation if already on maximal anti-hypertensive treatment.
	Continue as per schedule.	Continue as per schedule.
Proteinuria	1	Continue at same dose level.	Continue as per schedule.	Continue as per schedule.
	2-3	
Continue at same dose level if proteinuria is <2gm/24 hours.
 
If proteinuria is >2gm/24 hours, withhold until proteinuria is <2 g/24 hours.
 
Time of repeat urine collection is at investigator discretion.
 
Then, resume at the same dose level or reduce by 1 dose level as per investigator judgment.
	Continue as per schedule.	Continue as per schedule.
irAEs (except for endocrinopathies)	1	Continue at same dose level.	Continue as per schedule.	Continue as per schedule.
	2	Continue at same dose level.	Withhold until Grade ≤1. If Grade 2 event does not resolve to Grade 1 after holding for at least 2 cycles (8 weeks), permanently discontinue.	Withhold until Grade ≤1. If Grade 2 event does not resolve to Grade 1 after holding for at least 2 cycles (8 weeks), permanently discontinue.
	3-4	Hold treatment until Grade ≤1 and restart at same dose level.	Permanently discontinue.	Permanently discontinue.
Immune related hypothyroidism	1	Continue at same dose level.	Continue as per schedule.	Continue as per schedule.
	2	Continue at same dose level.	May hold until patient is on thyroid hormone supplementation or symptoms resolve to baseline.	May hold until patient is on thyroid hormone supplementation or symptoms resolve to baseline.

	3-4	Hold treatment until Grade ≤ 1 and restart at same dose level.	Hold until symptoms resolve to baseline or until Grade ≤ 1 while on thyroid supplementation. Patient should be referred to Endocrine.	Hold until symptoms resolve to baseline or until Grade ≤ 1 while on thyroid supplementation. Patient should be referred to Endocrine.

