Immune related diabetes	1	Continue at same dose level.	Continue as per schedule.	Continue as per schedule.
	2	Continue at same dose level.	Considering holding until patient is stabilized (Grade ≤ 1) on replacement therapy. Insulin should be initiated as default treatment rather than oral therapies. Patient should be referred to Endocrine.	Considering holding until patient is stabilized (Grade ≤ 1) on replacement therapy. Insulin should be initiated as default treatment rather than oral therapies. Patient should be referred to Endocrine.
	3-4	Hold treatment until Grade ≤ 1 and restart at same dose level.	Hold until patient is stabilized (Grade ≤ 1) on replacement therapy. Insulin should be initiated as default treatment rather than oral therapies. Patient should be referred to Endocrine.	Hold until patient is stabilized (Grade ≤ 1) on replacement therapy. Insulin should be initiated as default treatment rather than oral therapies. Patient should be referred to Endocrine.
Immune related colitis/diarrhea	1	Continue at same dose level.	Consider holding until symptoms resolve to baseline or until Grade ≤ 1 . Consider antidiarrheals if other causes are excluded.	Consider holding until symptoms resolve to baseline or until Grade ≤ 1 . Consider antidiarrheals if other causes are excluded.
	2	Continue at same dose level.	Hold until symptoms resolve to baseline or until Grade ≤ 1 . Steroids may be considered if indicated on an individual basis.	Hold until symptoms resolve to baseline or until Grade ≤ 1 . Steroids may be considered if indicated on an individual basis.
	3	Hold treatment until Grade ≤ 1 and restart at same dose level.	Hold until symptoms resolve to baseline or until Grade ≤ 1 . Administer steroids at 1-2 mg/kg/d prednisone or equivalent with taper over 4 weeks. Patient should be referred to Gastroenterology. Consider colonoscopy.	Hold until symptoms resolve to baseline or until Grade ≤ 1 . Administer steroids at 1-2 mg/kg/d prednisone or equivalent with taper over 4 weeks. Patient should be referred to Gastroenterology. Consider colonoscopy.
	4	Permanently discontinue.	Permanently discontinue.	Permanently discontinue.
Immune related pneumonitis	1	Continue at same dose level.	Hold if there is progression with repeat CT chest at 3-4 weeks and treat as Grade 2.	Hold if there is progression with repeat CT chest at 3-4 weeks and treat as Grade 2.

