	2	Continue at same dose level.	Hold until symptoms resolve to baseline or until Grade ≤ 1 . Administer steroids at 1-	Hold until symptoms resolve to baseline or until Grade ≤ 1 . Administer steroids at 1-

			2 mg/kg/d prednisone or equivalent with taper over 4 weeks. Consider Pulmonology consult. Monitor every 3-4 days, if no clinical improvement, treat as Grade 3.	2 mg/kg/d prednisone or equivalent with taper over 4 weeks. Consider Pulmonology consult. Monitor every 3-4 days, if no clinical improvement, treat as Grade 3.
	3-4	Permanently discontinue.	Permanently discontinue.	Permanently discontinue.
Immune related hepatitis	1	Continue at same dose level.	Continue as per schedule.	Continue as per schedule.
	2	Continue at same dose level.	Hold until symptoms resolve to baseline or until Grade ≤ 1 . Steroids may be considered if indicated on an individual basis.	Hold until symptoms resolve to baseline or until Grade ≤ 1 . Steroids may be considered if indicated on an individual basis.
	3-4	Permanently discontinue.	Permanently discontinue.	Permanently discontinue.

Table 3. Dose modifications for drug-related adverse events potentially associated with axitinib and not considered immune-related.

Toxicity	NCI CTCAE Grade	Axitinib
Diarrhea	1-2	Continue at same dose level.
	3	Hold until symptoms resolve to baseline or until Grade ≤ 1 . Then, resume at the same dose level or reduce by 1 dose level as per investigator judgment.
	4	Permanently discontinue.
Hemorrhage/bleeding	1	For CNS bleeding, permanently discontinue. For non-CNS bleeding, continue at same dose level.
	2	For pulmonary and GI bleed (other than hemorrhoidal bleeding or in setting of colitis), permanently discontinue. For other bleeding events, hold until symptoms resolve to baseline or until Grade ≤ 1 . Then, resume at the same dose level or reduce by 1 dose level as per investigator judgment.
	3-4	Permanently discontinue.
Palmar-plantar erythrodysesthesia syndrome	1-2	Continue at same dose level. Consider the use of topical pain relievers and/or moisturizing exfoliant creams.
	3	Hold until symptoms resolve to baseline or until Grade ≤ 1 . Consider the use of topical or parenteral pain relievers and/or moisturizing exfoliant creams. Then, resume at the same dose level or reduce by 1 dose level as per investigator judgment.
AST, ALT or bilirubin elevation	1	Continue at same dose level.
	2	Hold until symptoms resolve to baseline or until Grade ≤ 1 . Then, resume at same dose level.

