	3-4	Hold until symptoms resolve to baseline or until Grade ≤ 1 . Then, reduce by 1 dose level.
Hematologic abnormalities	1-3	Continue at same dose level.

	4	Hold until symptoms resolve to baseline or until Grade ≤1. Restart axitinib dose reduced by 1 dose level. Note: Grade 4 lymphopenia not associated with clinical events, (e.g, opportunistic infection) may continue on with axitinib.
Stevens-Johnson syndrome	3-4	Permanently discontinue.
Other non-hematologic toxicities and laboratory abnormalities	1-2	Continue at same dose level.
	3	Hold until symptoms resolve to baseline or until Grade ≤2. For toxicities controlled with symptomatic medications or asymptomatic laboratory abnormalities, continue at the same dose level or reduce by 1 dose level as per investigator judgment. For all other toxicities, reduce by 1 dose level.
	4	Hold until symptoms resolve to baseline or until Grade ≤2. Then, reduce by 1 dose level as per investigator judgment. Permanently discontinue axitinib for Grade 4 toxicities that meet any of the following conditions: 1) recurrent 2) life-threatening 3) reversible posterior leukoencephalopathy syndrome 4) arterial thrombosis/ischemia

4.2.4 Infusion related reactions.

Because avelumab and bavituximab are administered as infusions, infusion reactions are possible and may include symptoms such as fever, chills, shortness of breath, headache, and rigors. Infusion modifications depend on the severity of reactions as detailed in Table 4 below.

Table 4. Infusion-related reactions caused by avelumab or bavituximab.

NCI CTCAE Grade	Infusion modifications
1	Decrease the avelumab and/or bavituximab infusion rate by 50%.
2	Temporarily discontinue avelumab and/or bavituximab infusion. Resume infusion at 50% of previous rate once infusion-related reaction has resolved or decreased to at least Grade 1 in severity, and monitor closely for any worsening.
3-4	Stop the infusion immediately and disconnect infusion tubing from the patient. Patients may not receive further treatment.

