6.2 Safety/Tolerability

Analyses will be performed for all subjects having received at least one dose of study therapy. The study will use the CTCAE version 5.0 for reporting of adverse events. https://ctep.cancer.gov/protocolDevelopment/electronic_applications/ctc.htm

A safety lead-in phase composed of the first six patients evaluable for dose-limiting toxicities as defined in Section 4.2 will be performed to ensure the safety and tolerability of this triplet regimen.

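### A patient whose dose-limiting toxicity stops the Day 15 avelumab dose falls outside the lead-in's evaluable six, so the most disruptive early toxicities can go uncounted

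*Combined protocol and SAP*

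**What the plan says.** Section 4.2.1 places the safety and tolerability assessment after six DLT-evaluable patients have finished cycle 1. A patient is evaluable only if he or she has "completed all scheduled study visits during the first cycle and have received 2 (100%) of the 2 planned doses of avelumab" and has also received at least 3 of the 4 planned bavituximab doses. All conditions must be met, and none is waived for a patient who has had a DLT.

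A DLT is any treatment-related event of Grade 3 or higher in the 28 days of cycle 1, or an intolerable related Grade 2 gastrointestinal toxicity. With at most one DLT, "trial enrollment will proceed without any modifications". With two or more, the gastrointestinal disease-oriented team reviews the related events and considers modifying or ending the study.

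Other places repeat the restriction. Section 6.2 describes "A safety lead-in phase composed of the first six patients evaluable for dose-limiting toxicities as defined in Section 4.2", and Section 10.1 also refers back to Section 4.2. The Study Schema footnote reads: "The first 6 patients enrolled who have received at least 1 cycle of treatment will be considered a safety lead-in".

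**The concern.** A patient normally counts in a DLT assessment in one of two ways: by having a DLT, or by receiving enough treatment without one to be informative. The protocol applies the enough-treatment test to everyone. A toxicity severe enough to stop the infusions then disqualifies the patient in whom it occurred.

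For example, suppose two early patients have Grade 3-4 infusion reactions on Day 1 and receive nothing more. Neither is evaluable. If the six patients who do qualify have no DLT, the literal count is zero and the trial proceeds unchanged, although two treated patients had DLTs.

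The error can run in only one direction, because the exception is missing for patients with a DLT. It also concerns the only numerical toxicity rule for this triplet; the stopping rule in Section 7.6 covers futility alone.

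**Working it through.** **Which DLTs are lost.** Avelumab is given on Days 1 and 15 and bavituximab on Days 1, 8, 15 and 22 (Section 4.1). If related and occurring before the Day 15 infusions:

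- *Grade 3-4 infusion reaction.* Table 4 says: "Stop the infusion immediately and disconnect infusion tubing from the patient. Patients may not receive further treatment". The patient has at most 1 of 2 avelumab doses and is lost.
- *Grade 3-4 immune-related event.* Table 2 permanently discontinues both antibodies for non-endocrine events in general, and in separate rows for pneumonitis and for "Immune related hepatitis". The patient is lost.
- *Grade 3 event in the row* "Immune related colitis/diarrhea". Both antibodies are held until recovery. The patient is lost if the hold prevents a second avelumab dose within cycle 1.
- *Treatment-related death.* The patient is lost.

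**Which DLTs are kept.** Once the Day 15 infusions have been given with no earlier omission, the patient has 2/2 avelumab and 3/4 bavituximab doses, so a later DLT is lost only through a missed visit. Grade 3 hypertension (Table 2) and hand-foot syndrome (Table 3) change axitinib alone and remain counted.

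**Size.** The protocol gives no operating characteristics for the lead-in, so there is no stated figure to reproduce. Two quantities are assumed:

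- p = true probability that a patient has a cycle 1 DLT (at most one per patient);
- f = share of DLT patients who lose evaluability.

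If lost patients are replaced until six are evaluable, the DLT rate among evaluable patients is q = p(1 − f) / [p(1 − f) + (1 − p)], and P(proceed) = P(at most 1 DLT in 6) = (1 − q)^6 + 6q(1 − q)^5.

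Worked case, p = 1/3 and f = 0.25: q = 0.25 / (0.25 + 0.667) = 0.273, so P(proceed) = 0.727^6 + 6 × 0.273 × 0.727^5 = 0.148 + 0.333 = 0.481. With f = 0 it is 0.351.

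| p | f = 0 | f = 10% | f = 25% | f = 50% | f = 75% |
|---|---|---|---|---|---|
| 1/3 | 35% | 40% | 48% | 66% | 86% |
| 40% | 23% | 27% | 35% | 53% | 79% |
| 50% | 11% | 14% | 19% | 35% | 66% |

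For f of 10-25% the increase is 5-13 points at p = 1/3, 4-12 at p = 40% and 3-8 at p = 50%.

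**Without replacement.** If lost patients are not replaced and simply add nothing to the count among the six enrolled, the counted rate is p(1 − f). At p = 1/3 and f = 25% this is 0.25, and P(proceed) is 53% rather than 48%.

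**What the documents suggest about f.** With axitinib plus avelumab in 22 HCC patients, the commonest Grade 3 related events were hypertension (50.0%) and hand-foot syndrome (22.7%), with no Grade 4 or 5 events (Section 1.2.3). Both of these stay counted. With bavituximab plus pembrolizumab, Grade 3-4 colitis or diarrhea occurred in 2 of 36 patients and rash in 1 of 36 (Section 1.2.9). This points to the lower f columns, but neither source reports cycle 1 rates.

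**The case against.** The strongest reply is that the text can be read more generously. The two decision bullets refer to DLTs occurring, without restricting them to evaluable patients, and the DLT definition is not restricted either. The evaluable six could be taken to set only the timing of the assessment. Section 4.2 opens by making every treated subject evaluable for toxicity. Section 11.4 has the disease-oriented team and the data and safety monitoring committee review toxicity in real time, so nobody would fail to see an infusion-ending or fatal event.

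Part of this stands. The events are not hidden, the team could choose to count them, and reaching two DLTs triggers a review rather than a stop. But the general toxicity statement is a separate definition. Sections 6.2 and 10.1 define the lead-in as the first six DLT-evaluable patients, and nothing adds another patient's DLT to the threshold. The meaning of a go/no-go count should not be settled after the event.

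Four narrower points:

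- Replacement during the enrolment pause is not described, and the main table assumes it. Dropping that assumption enlarges the effect.
- Two DLTs in one patient would reach the threshold as the bullets are worded, so the table somewhat overstates P(proceed) if patients have several DLTs. It does not bring an excluded patient's events into the count.
- The ±3-day window means a short colitis hold need not cost the second avelumab dose. The other examples are unaffected.
- The f = 50% and 75% columns have no support in the cited data and only show the range.

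**Conclusion.** The concern holds: the evaluability rule is wrong as written. Followed literally, it removes from the lead-in count exactly those DLTs that end or suspend the antibody infusions early in cycle 1, or that are fatal, and so favours proceeding.

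The absence of an exception is certain from the text; the size is not. Over f of 10-25% and p from one third to one half, the chance of proceeding unmodified rises by about 3 to 13 percentage points. This rests on assumed p and f, replacement to six evaluable patients, and at most one DLT per patient. If axitinib-type DLTs prove frequent in cycle 1, review is likely either way: at p = 50% its probability is 89% with every DLT counted and 81% with f = 25%. This should be fixed, but it does not undermine the rest of the design.

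**What to change.** Redefine DLT-evaluable in Section 4.2.1 as either:

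- (a) any patient with a DLT in cycle 1 after any dose of study drug, whatever doses were received or visits completed; or
- (b) a patient without a DLT who completes cycle 1 and meets the existing visit and dose minimums (2/2 avelumab, at least 3/4 bavituximab).

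Replace only DLT-free patients who fail (b). State in the decision bullets that the count is taken over patients evaluable under (a) or (b), and leave the thresholds of at most one and two or more as they are. Align the Study Schema footnote. Sections 6.2 and 10.1 refer back to Section 4.2 and need no separate change.

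The cost is one paragraph of protocol wording and a somewhat higher chance that the disease-oriented team's review is triggered. Doses and toxicity-management tables are untouched.

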4.2.2 Axitinib dose reduction and re-escalation

Dosing interruption and/or dose reduction by 1, and if needed, 2 dose levels (one dose level decrease at a time) as indicated in Table 1 will be allowed depending on the type and severity of toxicity encountered. Patients who have undergone dose reduction may undergo dose re-escalation to prior dose levels in the absence of grade 2 or greater AEs for at least 28 days.

If patient develops decompensated cirrhosis (Child Pugh B), axitinib dosing should be reduced to the -1 dose level. Subsequent dosing can be increased or decreased according to the patient's tolerance. Patients must not have irreversible toxicities related to the axitinib to be eligible for dose re-escalation of axitinib after dose reduction.

Table 1. Axitinib dose levels.

Dose level	Dose
0	5 mg BID
-1	3 mg BID
-2	2 mg BID

Further dose reductions less than dose level -2 are not permitted.

4.2.3 Axitinib dose modifications, and avelumab and bavituximab infusion omissions for treatment-related toxicities.

Toxicities related to axitinib may primarily stem from the known on-target effects of inhibiting VEGFR including hypertension and proteinuria. In contrast, toxicities related to avelumab and bavituximab may be due to immune related AEs (irAEs). Management of specific irAEs should be consistent with American Society of Clinical Oncology (ASCO) Clinical Practice Guidelines (2018). For Grade 2 irAEs, avelumab and bavituximab should be permanently discontinued if AE does not resolve to at least Grade 1 within 12 weeks of last dose or corticosteroids cannot be reduced to ≤ 10 mg prednisone or equivalent per day within 12 weeks. Specific dose modifications and infusion omissions depend on the severity of toxicities as detailed in Table 2 and Table 3.

If any study drug is withheld or discontinued, the remaining study drugs can be continued as long as the patient is experiencing clinical benefit, as determined by the investigator per medical judgment.

Table 2. Dose modifications and infusion omissions for toxicities.

Toxicity	NCI CTCAE Grade	Axitinib	Avelumab	Bavituximab
Hypertension	1	Continue at same dose level.	Continue as per schedule.	Continue as per schedule.
	2	If not on maximal anti-hypertensive treatment, institute new or additional antihypertensive medication and continue at the same dose level. If on maximal anti-hypertensive treatment, reduce by 1 dose level.	Continue as per schedule.	Continue as per schedule.

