10.0 STATISTICAL CONSIDERATIONS

10.1 Study Design/Study Endpoints

The study is an open-label, non-randomized single-arm, multi-center phase II therapeutic clinical trial with a safety lead-in. The study population will be patients with advanced HCC.

Combination treatment with axitinib, avelumab, and bavituximab will be tested in a safety lead-in of the first 6 patients evaluable for dose-limiting toxicities in this study (see definitions for evaluable patients and dose-limiting toxicities in Section 4.2) to ensure the safety and tolerability of this triplet regimen.

A two-stage design is used to limit the maximum sample size required to determine efficacy. Objective response requires confirmation imaging greater than or equal to 4 weeks after initial best response. Patients who attain a complete response, partial response, or stable disease but do not have two imaging assessments to confirm response will be replaced. Patients who have progressive disease at any imaging assessment do not require subsequent confirmation.

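### Dose-limiting toxicity (DLT) evaluability sets a minimum Cycle 1 exposure for avelumab and bavituximab but none for axitinib, so DLT-free patients with low axitinib intake can help clear the triplet

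*Combined protocol and SAP*

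**What the plan says.** Section 10.1 gives the purpose of the lead-in as "to ensure the safety and tolerability of this triplet regimen"; Section 6.2 says the same. Section 4.2.1 defines who counts. The first condition concerns visits: "Patients will be considered evaluable for dose-limiting toxicities assessment if they have completed all scheduled study visits during the first cycle". The second concerns drug exposure: patients must "have received 2 (100%) of the 2 planned doses of avelumab and at least 3 (75%) of the 4 planned doses of bavituximab". Axitinib is not mentioned in either condition. Sections 6.2 and 10.1 refer back to Section 4.2 for the definition. The Study Schema footnote asks only for one cycle of treatment, with no minimum for any drug.

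With 0 or 1 DLT among the six, "trial enrollment will proceed without any modifications". With two or more, the GI disease-oriented team (GI DOT) considers changing or ending the study, and the one change named is "reducing the starting dose of axitinib by one dose level to 3 mg BID".

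Axitinib is planned twice daily without a break (Section 4.1.5). Section 4.2.3 adds that "If any study drug is withheld or discontinued, the remaining study drugs can be continued", provided the investigator judges that the patient is benefiting clinically.

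**The concern.** The lead-in asks whether patients tolerate three drugs together. A patient who received little of one of them carries less information on that question, yet enters the count on the same footing as a fully exposed patient. The protocol already applies this principle to the two infusions. It leaves it out for the drug that its own remedy would adjust.

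The missing criterion could matter because the protocol's avelumab plus axitinib data (Section 1.2.3, 22 patients) show Grade 3 treatment-related hypertension in 50.0% and hand-foot syndrome in 22.7%, and Section 4.2.3 names hypertension as an on-target axitinib effect. If low axitinib intake lowers a patient's chance of a DLT, each such patient among the six makes the outcome of no modification more likely. At stake is how much weight a favourable lead-in result can bear. How patients who do have a DLT are handled is a separate matter.

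**Working it through.** **Figures stated in the plan.** The documents give no operating characteristics for the six-patient rule. The only stated design figures are for response rate (Section 10.2): 14 then 15 patients, continue at 2 or more responses, reject at 7 or more of 29. The exact rejection probability is the sum over x = 2 to 14 of Bin(x; 14, p) × P(Bin(15, p) ≥ 7 − x). This gives 0.0973 at p = 0.14 and 0.9002 at p = 0.34, which agrees with the stated 0.10 limit and 0.9 power. The present point does not affect that design.

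**How low intake can arise without a DLT.** Planned Cycle 1 axitinib is 28 × 2 = 56 doses. A DLT is a related event of Grade 3 or higher, or an intolerable related Grade 2 gastrointestinal toxicity (Section 4.2.1).

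- Missed or vomited doses are not made up (Section 4.1.5). No limit on their number affects evaluability.
- Procedures (Section 4.3.3): a stop of at least 24 hours before and 7 days after minor surgery is about 2 + 14 = 16 doses, leaving 40 of 56 (71%). After major surgery, 2 to 3 weeks gives 2 + 28 = 30 to 2 + 42 = 44 doses missed, leaving 26 to 12 of 56. Delaying the infusions is left to the investigator.
- Holds below DLT level (Table 3): a Grade 2 AST, ALT or bilirubin elevation holds axitinib. The metabolic panel is scheduled on Days 1 and 15, so a hold starting at Day 15 and lasting to the end of the cycle leaves about 28 of 56 doses (50%).
- Table 3 also stops axitinib permanently for Grade 2 pulmonary bleeding, which is below the DLT threshold.

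**Effect on the clearing rule.** Let p be the DLT probability at full exposure, q the probability in a low-axitinib patient, and k the number of such patients among the six. Assuming independence between patients:

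P(0 or 1 DLT) = (1−p)^(6−k) (1−q)^k + (6−k) p (1−p)^(5−k) (1−q)^k + k q (1−q)^(k−1) (1−p)^(6−k)

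With p = 0.33 (assumed):

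- k = 0: 0.0905 + 0.2673 = 0.358
- k = 1, q = 0.10: 0.1215 + 0.2992 + 0.0135 = 0.434
- k = 1, q = 0.05: 0.1283 + 0.3159 + 0.0068 = 0.451
- k = 2, q = 0.10: 0.1632 + 0.3216 + 0.0363 = 0.521
- k = 2, q = 0.05: 0.1819 + 0.3583 + 0.0191 = 0.559

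With p = 0.50 and the same range for q, the values are 0.109 (k = 0), 0.172-0.180 (k = 1) and 0.264-0.288 (k = 2). The probability falls as any one patient's DLT probability rises, so for every q below p the shift is toward clearing.

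**The case against.** The case on the other side has substance.

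- A reader might infer that a patient with no axitinib at all could count. The documents do not support that: Section 4.2.1 opens with "A safety and tolerability assessment will be performed for patients treated with axitinib, bavituximab, and avelumab after the first 6 patients evaluable", so some intake is implied. It sets no amount, however, so low intake remains allowed.
- Most protocol-driven holds leave partial exposure. Urinalysis is scheduled on Day 1 only, so a proteinuria hold would usually come too late to affect Cycle 1. Table 3 covers events not considered immune-related. If a Grade 2 liver event is judged immune-related, Table 2 holds the two antibodies instead, which may make the patient non-evaluable.
- A patient who stops axitinib for a related Grade 3 event and meets the visit and infusion conditions is counted as a DLT, so that route does not dilute the result.
- A reader might also assume that low-axitinib patients cannot have a DLT. With a rate of 1/3 in the others, that would put the chance of clearing at 0.59 with two such patients and 0.74 with three. The documents do not support a zero rate: a DLT may be attributed to any of the drugs, Section 7.2.2 warns of severe infusion and immune-related reactions with avelumab, and bavituximab plus pembrolizumab produced Grade 3 or 4 colitis or diarrhea in 5.6% (Section 1.2.9). Nor do they support two or three such patients as an expectation.
- Enrollment is suspended until the GI DOT finishes its assessment, toxicity is evaluated in every treated patient, and Section 11.4 provides real-time review. The team could look at axitinib exposure, but nothing requires it to, and the stated outcome at 0 or 1 DLT is unconditional.

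These points limit the size of the problem. None of them supplies the missing criterion.

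**Conclusion.** The omission is certain from the text; its effect is not. Under assumed DLT rates of 0.33 at full exposure and 0.05-0.10 at low axitinib exposure, one low-intake patient raises the chance of clearing by about 8 to 9 percentage points, and two raise it by about 16 to 20. These are illustrations. The documents give neither a Cycle 1 DLT rate nor an expected number of low-intake patients, and the 50.0% and 22.7% figures are not limited to Cycle 1.

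A reader might conclude that the lead-in leaves the triplet's tolerability unanswered. That goes too far: the other safety reviews continue, and typical interruptions leave a good part of the axitinib dose taken. The supported conclusion is narrower. The stated rule allows a tilt toward proceeding unmodified, and it can be closed cheaply with data already collected.

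**What to change.** In Section 4.2.1, add a minimum proportion of planned Cycle 1 axitinib to the evaluability conditions for DLT-free patients. The sponsor should set the threshold; 75% would mirror the bavituximab rule.

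Measure it as cumulative dose from tablet counts and the diary, not as number of doses. Planned intake is 56 × 5 mg = 280 mg. A patient on 3 mg twice daily throughout would take all 56 doses but only 168 mg (60%), which a count of doses would miss.

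Treat patients below the threshold according to the reason:

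- For reasons other than drug-related toxicity: replace the DLT-free patient for the DLT count only. The patient stays in the trial.
- Because of drug-related toxicity: keep the patient in the assessment and report the patient to the GI DOT with the axitinib exposure, since the low intake is itself tolerability information.

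Align the Study Schema footnote with this definition, and make sure the wording on suspending enrollment allows a replacement to be entered.

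The cost is protocol wording. Tablet counts (Section 8.1.1) and the diary (Section 4.1.5, Appendix A) are already collected, and the response-rate design does not change. One or two lead-in patients may need replacing, which could lengthen the lead-in by about a cycle.
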